# 6.4.12 IMP disposal

All unused and used IMP vials should be retained at the center until accountability and reconciliation has been performed by the study monitor. At the end of the treatment period, any unused IMP will either be destroyed at the investigator site or be returned to the sponsor/designee for destruction, and destruction will be documented appropriately. If no supplies remain, this fact will be documented appropriately.

# Baseline, efficacy, safety, pharmacokinetic, pharmacodynamic and pharmacogenetics assessments

# 6.5.1 Medical history

Medical history will be recorded at screening. Investigators should document the occurrence, signs, and symptoms of the patient's preexisting conditions, including all prior significant illnesses, up to and including 1 year before enrollment in the study. Additional preexisting conditions that started before and are ongoing at the date of enrollment are to be regarded as current medical conditions. Medical history will include alcohol consumption and smoking history, if applicable.

Information about HSCT and related complications will be also collected, including underlying disease diagnosis; donor type; HLA mismatch; stem cell source; type and start date of conditioning regimen; conditioning medications; date of transplant; transplant manipulation; donor chimerism; date of confirmed engraftment; GVHD date of onset; GVHD grade according to the International Bone Marrow Transplant Registry severity Index [22]; presence of infections; presence of donor specific antibodies; posttransplant treatments and date (e.g., donor lymphocyte infusion, stem cell boost, growth factors; infusion of antiviral T cells); GVHD prophylaxis.

Information about TA-TMA will be collected including date of diagnosis (defined as the earliest date when all required laboratory criteria outlined in Inclusion Criterion #3 are met); diagnostic laboratory markers; initial management; and presence of signs and symptoms of end organ injury.

Baseline end organ injury will be evaluated as follows, with associated medications:

Confidential Page 46 of 89

- a. Kidney: doubling of serum creatinine compared with pre-HSCT level or patient receiving renal replacement therapy or proteinuria ≥ 30 mg/dL OR rUPCR ≥ 1 mg/mg.
- b. Lungs: hypoxemia or any need for noninvasive or invasive positive pressure ventilation.
- c. Cardiovascular: pulmonary hypertension diagnosed by a cardiologist using cardiac catheterization, or pulmonary hypertension criteria on echocardiography or arterial hypertension, defined by systolic BP  $\geq$  140 mmHg and/or diastolic BP  $\geq$  90 mmHg at baseline or hypertension requiring > 2 medications (excluding diuretics).
- d. Serositis: clinically significant pleural effusion or pericardial effusion requiring surgical therapy (e.g., pericardiocentesis/ thoracocentesis).
- e. CNS: seizures attributable to posterior reversible encephalopathy syndrome.
- f. GI tract: presence of biopsy-proven GI TA-TMA. Patients with GI bleeding (hematemesis or hematochezia) will be excluded.

Illnesses first occurring or detected during the study and worsening of a concomitant illness during the study are to be documented as AEs on the eCRF in accordance with Section 6.5.5.1.2.

## 6.5.1.1 Vaccines medical history

Patients should be vaccinated against *N. meningitidis* (Types A, C, W, Y, and B) either within 2 years prior to Day 1 or, if clinically feasible, according to institutional guidelines for immune reconstitution after HSCT. Patients should be re-vaccinated against *H. influenzae* Type B and *S. pneumoniae*, if clinically feasible, according to institutional guidelines for immune reconstitution after HSCT. Received vaccines with dates will be recorded in the eCRF.

## 6.5.2 Demography

Demographic data, including age, sex, race and ethnicity, will be collected for all patients, as allowed, per applicable regulations and recorded in the eCRF.

## 6.5.3 Biopsy samples of affected organs

Diagnosis of TA-TMA may be established by histologic evidence of microangiopathy in any biopsied organ. Biopsy of affected organs is optional. In the case that any biopsy sample results are available prior to screening (up to 1 month before), these results can be used to confirm diagnosis.

#### 6.5.4 Pharmacokinetic assessments

Blood sampling and processing blood samples for the PK assessment of pegcetacoplan will be collected via direct venipuncture at the time points outlined in the schedule of assessments (Table 1). Should the patient have a central catheter already in place, in order to minimize patient

Confidential Page 47 of 89

Pegcetacoplan/TA TMA

Clinical Study No: Sobi.PEGCET-201

discomfort, the central line can be used to collect PK samples, except for the 15 and 30 minutes postdose samples.

On dosing Days 1, 3 and 5, PK samples will be taken up to 30 minutes predose and at 15 minutes ( $\pm$  5 min), 30 minutes ( $\pm$  5 min), 1 hour ( $\pm$  10 min), 4 hours ( $\pm$  10 min), 8 hours ( $\pm$  30 min), and 24 hours ( $\pm$  30 min) postdose. From Day 8 and onwards, PK samples will be taken predose at all other visits.

Instructions for collection, handling, processing, storage and shipping of samples will be provided in a separate sample handling manual prior to study initiation.

Serum sample analysis will be performed using validated liquid chromatography tandem mass spectrometry methods. The methods used and the results obtained will be included in the CSR as an appendix.

## 6.5.4.1 Pharmacokinetic parameters

PK parameters for pegcetacoplan will be computed from the individual serum concentration-time data, using actual sample times using a non-compartmental approach. Appropriate validated PK software (e.g., Phoenix WinNonlin®) will be used.

The following PK parameters will be calculated:

#### induction phase:

- AUC0-tau: area under the concentration-time curve over the dosing interval.
- Cmax: maximum observed serum concentration.
- $T_{max}$ : time of the maximum measured serum concentration. If the maximum value occurs at more than 1 time point,  $T_{max}$  is defined as the first time point with this value.

#### s.c. maintenance phase:

• Ctrough: observed serum concentration predose.

#### 6.5.5 Safety assessments

#### 6.5.5.1 Adverse events

#### 6.5.5.1.1 Definitions

#### Adverse event

An AE is any untoward medical occurrence in a patient or study patient administered a pharmaceutical product; the event does not necessarily have a causal relationship with the treatment or usage.

AEs include the following:

- Abnormal test findings, as specified below.
- Changes in physical examination findings.

Confidential Page 48 of 89

Pegcetacoplan/TA TMA

- Clinical Study No: Sobi.PEGCET-201
- Progression/worsening of underlying disease.
- Signs and symptoms resulting from overdose, withdrawal of treatment, drug-drug interactions, abuse and misuse.
- Increase in frequency or intensity of a preexisting episodic disease or medical condition.
- Disease or medical condition detected or diagnosed during the course of the study even though it may have been present prior to the start of the study.
- Continuous persistent disease or symptoms present at study start that worsen following the start of the study.

For pregnancies and breastfeeding, see Section 6.5.5.1.5.

## **Abnormal test findings**

An abnormal test finding, e.g. abnormal laboratory analysis results, vital signs or ECG, should be recorded as an AE in any of the following situations:

- The investigator considers the abnormal test finding to be clinically significant.
- The abnormal test finding leads to a medical/surgical intervention including withdrawal of IMP(s) or discontinuation from the study. Repeat/confirmatory testing is not considered a medical intervention.

#### **Preexisting conditions**

A preexisting condition (i.e., a disorder present before the AE reporting period started and noted on the pretreatment medical history/physical examination form) should not be reported as an AE unless the condition worsens or episodes increase in frequency during the AE reporting period.

#### AEs diagnosis versus signs/symptoms

For any AE, a diagnosis should be recorded rather than individual signs and symptoms or abnormal laboratory findings. However, if at the time of AE reporting a diagnosis is not available, each individual sign/symptom should be recorded. If a diagnosis is subsequently established, all previously reported AEs based on signs and symptoms should be removed and replaced by one AE report based on the single diagnosis, with a starting date that corresponds to the start date of the first symptom of the eventual diagnosis.

#### **Procedures**

Diagnostic and therapeutic noninvasive and invasive procedures, such as surgery, should not be reported as AEs. However, the medical condition for which the procedure was performed should be reported if it meets the definition of an AE. For example, an acute appendicitis that begins during the AE reporting period should be reported as the AE and the resulting appendectomy entered in the comments section of the eCRF.

Confidential Page 49 of 89

Pegcetacoplan/TA\_TMA

Clinical Study No: Sobi.PEGCET-201

#### Treatment-emergent adverse event

A treatment-emergent AE is any AE temporally associated with the use of study treatment, i.e., from study treatment initiation until 8 weeks after study treatment discontinuation.

#### Serious adverse event

An AE that meets one or more of the following criteria/outcomes is classified as serious:

- Results in death.
- Is life-threatening (i.e., at immediate risk of death).
- Requires in-patient hospitalization or prolongation of existing hospitalization.
- Results in persistent or significant disability/incapacity.
- Is a congenital anomaly/birth defect (i.e., in an offspring to the study patient).
- Is a medically important AE.

Medically important AEs are events that may not result in death, be life-threatening, or require hospitalization but may be considered serious when, based upon appropriate medical judgment, may jeopardize the patient or patient or may require medical or surgical intervention to prevent one of the outcomes listed above. Examples of such events are intensive treatment in an emergency room or at home for allergic bronchospasm, blood dyscrasias or convulsions that do not result in hospitalization or development of dependency or abuse.

Serious also includes any other event that the investigator or company judges to be serious. Any suspected transmission of an infectious agent via IMP shall also be considered serious.

#### Hospitalization

In general, hospitalization means that the patient has been detained (usually involving at least an overnight stay) at the hospital or emergency ward for observation and/or treatment that would not have been appropriate in the physician's office or outpatient setting. When in doubt as to whether hospitalization occurred or was necessary, the AE should be considered serious.

The following situations are not considered hospitalizations (although other SAE criteria may still apply):

- Outpatient procedures/ambulatory care.
- Emergency department visits.

Hospitalization in the absence of an AE occurring during the study should not be considered an SAE. This includes:

- Pre-planned hospitalization due to a preexisting condition not associated with a worsening of the preexisting condition.
- Protocol specified admission.

Confidential Page 50 of 89

Pegcetacoplan/TA TMA

Clinical Study No: Sobi.PEGCET-201

• Elective admission, e.g. due to cosmetic surgery.

Complications that occur during hospitalization should not be considered SAEs unless the complication prolongs hospitalization.

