### 6.1.5 Stopping criteria

In the context of this study, the term toxicity means clinically significant drug related adverse reaction(s). In case of serious toxicity defined as a Grade 4 to 5 SAE, an ad hoc SRC meeting will be held within 24 hours after Sobi awareness of the AE. The SRC will decide on the impact on an individual or entire study level, continue study unchanged, continue study with modifications, or to put the study on hold.

Standard toxicity grading according to the NCI-CTCAE are used to grade AEs and to decide on suspension level:

- The study will be halted if a patient develops a Grade 5 SAE suspected to be IMP related.
- The treatment will be halted if 2 patients experience a similar drug-related Grade 4 SAE.
- Study treatment will be discontinued on an individual level if assessment by an ad hoc SRC or the investigator conclude significant risk to the patient's safety.

Confidential Page 34 of 89

Pegcetacoplan/TA\_TMA

Clinical Study No: Sobi.PEGCET-201

Grade 4	Life-threatening consequences; urgent intervention indicated
Grade 5	Death

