## 6.4.5 Selection and timing of doses for each patient

Pegcetacoplan will also be administered by the investigator's site staff as long as the patient is hospitalized. If deemed by the investigator that a patient can be discharged from hospital upon clinical improvement, pegcetacoplan administration will occur at home. Patients will self-administer s.c. IMP, after receiving appropriate training by research personnel.

When the patient's pegcetacoplan dosing schedule aligns with study visit days, pegcetacoplan should be administered at the study site and the study procedures should be completed as outlined in this protocol (Table 1). In some instances, however, a patient may not be able to align the date of a study visit with his/her pegcetacoplan administration schedule (e.g., if the patient has to utilize the visit window in order to be able to attend a study visit). In such instances it is important that pegcetacoplan dosing occurs according to the dosing schedule and not the visit schedule.

Patients will be instructed to self-administer pegcetacoplan only as prescribed and to contact the investigator immediately for guidance in the event of any missed doses.

Dosing diaries will be used for study treatment and are to be completed for each dose administered at the clinic or at home. Patients should not deviate from the every-3-days dosing schedule.

The preferred site of s.c. infusion will be the abdomen. If administration into the abdomen is not feasible, alternative appropriate sites are acceptable (see the Pump Instructions for Use document for more details).

Pegcetacoplan will be administered using a syringe pump. Details of infusion volume and time will be detailed in the pharmacy manual.

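### The protocol's sentence on in-hospital complications contradicts its own SAE definition, so a life-threatening inpatient event could go unclassified as an SAE and miss the triggers that count SAEs

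*Protocol*

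**What the plan says.** Protocol Section 6.5.5.1.1 defines seriousness by a list of alternatives: "An AE that meets one or more of the following criteria/outcomes is classified as serious". The list opens with "Results in death". Life-threatening events, hospitalization or its prolongation, lasting disability, congenital anomaly and medical importance are separate items.

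A sub-heading, Hospitalization, then explains one of those items. It contains three statements of exclusion:

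- Outpatient care and emergency department visits. This list is introduced with a caveat: "The following situations are not considered hospitalizations (although other SAE criteria may still apply".
- Admissions with no adverse event behind them, such as planned or elective stays.
- The closing sentence: "Complications that occur during hospitalization should not be considered SAEs unless the complication prolongs hospitalization". It carries no caveat.

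Section 6.1.5 uses the SAE label for its study-level actions: "In case of serious toxicity defined as a Grade 4 to 5 SAE, an ad hoc SRC meeting will be held within 24 hours" of the sponsor learning of the event, and "The study will be halted if a patient develops a Grade 5 SAE suspected to be IMP related". Treatment is also halted once two patients have similar drug-related SAEs of Grade 4. That section describes Grade 4 as life-threatening and Grade 5 as death.

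On where patients are when dosed, Section 6.4.5 says: "Pegcetacoplan will also be administered by the investigator's site staff as long as the patient is hospitalized".

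**The concern.** The closing sentence does not say that an in-hospital complication fails the hospitalization criterion. It says that the complication is not an SAE. A site applying those words to an inpatient with a life-threatening reaction that resolves within the expected stay would record a non-serious AE.

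Three things hang on the label:

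- the 24-hour report to the sponsor (Section 6.5.5.1.4);
- the SAE tables (Protocol Section 8.3.3.2, SAP Section 8.9.1);
- the ad hoc committee meeting and the two halts in Section 6.1.5.

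The setting makes this practical. Section 6.4.4 describes TA-TMA as acute and life-threatening, and home dosing begins only after discharge on clinical improvement. Section 4.3 reports a strong causal association with hypersensitivity and a potential risk of infection with encapsulated bacteria. Such reactions may well occur in patients who are already in hospital.

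**Working it through.** No figure in the documents bears on this point, so the check is a comparison of texts followed by a sensitivity illustration on assumed rates.

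**1. Where the two rules agree and where they do not (Section 6.5.5.1.1).**

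| In-hospital AE | Seriousness definition | Closing sentence under Hospitalization |
|---|---|---|
| Prolongs the stay | SAE | SAE |
| Does not prolong the stay, meets no other criterion | Not an SAE | Not an SAE |
| Does not prolong the stay, but is life-threatening, disabling or medically important | SAE | Not an SAE |

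The third row is the contradiction. No text gives either rule precedence. The caveat earlier under the same sub-heading shows that the authors knew how to keep the other criteria alive, but it is attached to a different list.

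**2. What follows if the closing sentence is applied.** In Section 6.1.5, the ad hoc meeting needs a Grade 4 to 5 SAE, the study halt needs a Grade 5 SAE suspected to be related, and the treatment halt needs two similar related Grade 4 SAEs. An event in the third row counts toward none of them. The fourth provision, individual discontinuation on judged risk, does not use the label.

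**3. What still captures the event.** All AEs are recorded up to 8 weeks after the last dose (Section 6.5.5.1.2), so it remains a TEAE. Scheduled committee reviews come after the first patient's 4 weeks, after the first 3 patients' 12 weeks, and then every 6 months (Section 6.5.5.9), which is not equivalent to a 24-hour trigger. Section 6.1.5 refers to NCI-CTCAE grades, but Section 6.5.5.1.3 and the SAP tables use mild, moderate and severe. In those tables a life-threatening event not flagged as an SAE would appear simply as severe.

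**4. Sensitivity of the Grade 4 trigger (assumed values, not from the documents).** Let n = 12, let q be the per-patient probability of a related Grade 4 event, and let m be the share of such events left out of the SAE count. Treat patients as independent and all these events as similar. With e = q(1 − m),

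P(at least 2 counted) = 1 − (1 − e)^12 − 12e(1 − e)^11.

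| q | m = 0 | m = 0.25 | m = 0.5 |
|---|---|---|---|
| 0.10 | 0.341 | 0.226 | 0.118 |
| 0.20 | 0.725 | 0.557 | 0.341 |
| 0.30 | 0.915 | 0.789 | 0.557 |

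For q = 0.10 and m = 0.5, e = 0.05 and the result is 1 − 0.540 − 0.341 ≈ 0.118. The table shows only that a two-patient trigger in 12 patients is sensitive to undercounting. It does not estimate how often undercounting would happen.

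**The case against.** The best defence is context. The sentence sits under a sub-heading that explains one criterion, so it can be read as saying only that already being in hospital does not satisfy that criterion. The SUSAR definition also requires at least one seriousness criterion, in line with the general rule. In addition, the seriousness text lets the investigator or the company judge any other event serious, so the sponsor can upgrade an event that a site has misread. Many sites would report correctly. This stands as far as it goes: the text is contradictory, and inpatient events are not definitively excluded. It does not remove the problem, because it relies on discretion to override an explicit instruction.

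Three stronger readings are tempting, and the documents do not support them.

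- *Inpatient deaths escape the stopping rule.* A reader might argue that death ends a stay and does not prolong it. But death heads the list of criteria, and a site would have to ignore that item. Date and reason for death are collected separately (Section 6.5.7.3), and deaths are summarized and listed (SAP Section 8.9.6). The life-threatening event that does not prolong the stay is the sounder example.
- *The primary safety objective is biased downward.* The endpoint in Section 5.1.2 is occurrence of TEAEs, which does not depend on seriousness. The effect is confined to SAE-specific tables, expedited reporting and the SAE-based triggers.
- *The trial's only toxicity safeguard fails.* Individual discontinuation rests on judged risk (Section 6.1.5), interruption for toxicity rests on investigator judgment (Section 6.4.6), and ad hoc committee meetings can be requested (Section 6.5.5.9). None needs an SAE label.

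**Conclusion.** The concern holds as an internal contradiction in the SAE definition that reaches the study-level triggers. Two conditions must be met for harm: a site applies the closing sentence literally, and the event is serious on another criterion without prolonging the stay. The protocol neither rules this out nor settles it.

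The size can be stated only structurally. One related Grade 5 SAE, or two similar related Grade 4 SAEs, among 12 patients triggers a halt. A single misclassified event can therefore decide whether a halt occurs, but only if no other qualifying event meets the threshold. The share of treatment time spent in hospital and the rate of misreading are not given, so no frequency follows from the documents.

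**What to change.** 1. Reword the closing sentence under Hospitalization so that it explains that criterion alone. For example: a complication arising during a hospital stay is an SAE if it prolongs the stay or meets any other seriousness criterion in this section.
2. Reconcile Section 6.1.5 with the two parts of Section 6.5.5.1.1, so that it is clear which classification its triggers rely on. This is a request for consistency and proposes no new stopping rule.
3. Before database lock, check every recorded inpatient AE not flagged as serious against all the seriousness criteria, using source documents where inpatient status is unclear. Report any SAE found late, and record whether any Section 6.1.5 trigger should have been considered. SAP Section 10 describes recruitment of the last patients in the past tense, so this check is probably where most of the remaining value lies.

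The cost is one sentence in an amendment or clarification letter, a review covering 12 planned patients, and possibly a few more SAE reports. The analysis methods do not change.

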#### Suspected unexpected serious adverse reaction

A SUSAR is an untoward and unintended response to a study drug that is not listed in the reference safety information of the IB, meets at least 1 of the seriousness criteria, and is assessed as causally related to the IMP.

#### 6.5.5.1.2 Adverse event reporting period

The AE/SAE reporting period will be as follows:

Screening period: Any SAEs occurring between signing of the ICF and the first IMP dose should be reported to Sobi.

Treatment period: All AEs (including SAEs) occurring upon receiving the first IMP dose up to 8 weeks after last IMP administration must be recorded in the AE pages of the eCRF. In addition, SAEs should be reported to Sobi.

Follow-up period: New SAEs occurring at any time after the 8-week AE follow-up period up to EOS should be reported to Sobi only if considered causally related to previous exposure to the IMP by the investigator. These SAEs are only entered in the drug safety database and, hence, will not affect study closure.

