- k β-HCG for women of childbearing potential and FSH for postmenopausal women. For women of childbearing potential, a serum pregnancy test will be performed at screening. Urine pregnancy tests will be performed at all subsequent site visits. Patients with positive results will be excluded or discontinued from the study.
- m All AEs occurring upon receiving the first IMP dose up to 8 weeks after last IMP administration must be recorded in the eCRF. SAEs will be reported from signing of the ICF up to 8 weeks after last IMP administration. New SAEs occurring at any time after the 8-week AE follow-up period up to EOS should be reported only if considered causally related to previous exposure to the IMP by the investigator.

Confidential Page 20 of 89

Pegcetacoplan/TA\_TMA Clinical Study No: Sobi.PEGCET-201

o An EOT/ET visit will be performed 4 weeks after the last dose of pegcetacoplan. For patients who complete 12 weeks of treatment, the EOT visit will be at Week 16, and there will be further follow-up visits at Weeks 20 and 24. For patients who complete 16 weeks of treatment, the EOT visit will be at Week 20 and there will be a further follow-up visit at Week 24. The main analysis will be performed after all patients have completed their Week 24 visit.

p Blood collection for safety laboratory tests at Day 1 can be omitted if screening samples were collected on Day -1.Note: On dosing days, all blood samples will be collected predose. The date and time of the sample and the date and time of the previous dose of pegcetacoplan must be recorded in the eCRF.

Note: Unscheduled additional visits may be performed at the investigator's judgment. Any of the study procedures or other assessments may be performed at the unscheduled visit at the discretion of the investigator.

Confidential Page 21 of 89

Pegcetacoplan/TA\_TMA

Clinical Study No: Sobi.PEGCET-201

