### 6.1.3 Follow-up period (up to 12 weeks)

After completion of the treatment period, all patients will enter in the follow-up period until Week 24. This includes an End of treatment visit 4 weeks after the last IMP dose and 1 or 2 more follow-up visits every 4 weeks for patients who have completed 16 or 12 weeks of treatment, respectively. The main analysis will be performed after all patients have completed their Week 24 visit.

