## 6.5.5.1.4 Serious adverse event reporting

Both serious and nonserious AEs are to be reported on the AE page of the eCRF as specified in the eCRF instructions.

In addition, all SAEs must be reported by the investigator to the Sobi Global Pharmacovigilance & Patient Safety within 24 hours of the investigator's first knowledge of the event.

If an SAE occurs, it is to be reported by e-mail (e-mail address is indicated on the SAE form) using the designated Serious Adverse Event form.

The SAE collection form is not always the same as the AE eCRF form. The forms must be completed in a consistent manner. For example, the same AE term should be used on both forms.

All new information obtained, relevant to an SAE report, should be forwarded to Sobi Global Pharmacovigilance & Patient Safety within the same timeframe as the initial information.

If the patient is hospitalized in a hospital other than the study site, it is the investigator's responsibility to contact this hospital to obtain all SAE-relevant information and documentation.

New SAEs occurring after the 8-week AE follow-up period must be reported to Sobi Global Pharmacovigilance & Patient Safety within 24 hours of the investigator's knowledge of the event, only if considered causally related to previous exposure to the study treatment by the investigator.

The investigator shall provide Sobi Global Pharmacovigilance & Patient Safety with sufficient information to enable a complete medical assessment of the reported event. Best efforts shall be made by the investigator to provide Sobi Global Pharmacovigilance & Patient Safety with additional information related to any SAE as requested.

The reference safety document to assess expectedness of a suspect serious adverse reaction and reported by the sponsor to Health Authorities, IRBs/IECs, and investigators is the reference safety information section of the IB.

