8.9.1 ADVERSE EVENTS

All AEs will be coded using MedDRA version current at the time of the DBL.

Pre-treatment AEs are those occurring between the ICF signature and the first IMP administration. TEAEs are defined as those AEs that start or worsen after the first dose of IMP and up to 8 weeks after the last IMP dose. Events will be flagged as treatment-emergent unless sufficient data are available to conclude that the start/worsening occurred before the treatment was started.

If the severity or relationship is missing for one of the treatment-emergent occurrences of an adverse event for a patient, the maximal severity or relationship on the remaining occurrences will be considered. If the severity is missing for all the occurrences, a "missing" category will be added in the summary table.

An overall summary table of the number and percentages of patients within the following categories will be provided:

- Any TEAE,
- Any related TEAE,
- Any serious TEAE,
- Any related serious TEAE,
- Any non-serious TEAE,
- Any related non-serious TEAE,
- Any TEAE leading to withdrawal of pegcetacoplan,
- Any serious TEAE leading to withdrawal of pegcetacoplan,
- Any TEAE leading to drug interruption,
- Any TEAE that is considered as a Target Medical Event as defined in Table 2 Definition of Target Medical Events,
- Any TEAE leading to death.
- Any TEAE that were infusion site reactions (as per eCRF, both injection and infusion site reactions

will be included).

- Any device related TEAEs (as per eCRF),
- Any TEAE by severity (mild, moderate and severe).

Pre-treatment AEs will be listed.

TEAEs, serious TEAEs, non-serious TEAEs, TEAEs by severity (mild, moderate, and severe), TEAEs related to pegcetacoplan, TEAEs leading to the withdrawal of pegcetacoplan, TEAEs leading to drug interruption, TEAEs that are considered as Target Medical Events, TEAEs that were infusion site reactions, device related TEAEs and AEs leading to death will be summarized by SOC and PT. Three categories of selected target TEAEs (Target Medical Events, defined in Table 2 - Definition of Target Medical Events) that are considered as Target medical Events will be summarized a posteriori. Summaries will include incidence of AEs, and number of events. The severity of AEs and the relationship to the IMP will be summarized for each SOC and PT.

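### Non-fatal related SAEs starting more than 8 weeks after the last dose reach no planned AE or SAE table or listing, although follow-up runs to Week 24

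*Protocol*

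**What the plan says.** Protocol 6.5.5.1.2 divides safety reporting after the first dose into two stages.

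- **Up to 8 weeks after the last dose.** All AEs, serious or not, "occurring upon receiving the first IMP dose up to 8 weeks after last IMP administration must be recorded in the AE pages of the eCRF".
- **From then to End of Study (EOS).** "New SAEs occurring at any time after the 8-week AE follow-up period up to EOS should be reported to Sobi only if considered causally related"; the investigator makes that judgement about the IMP. The section then states: "These SAEs are only entered in the drug safety database and, hence, will not affect study closure".

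Footnote m to Table 1 (Schedule of assessments) repeats the related-only rule for the late stage: "New SAEs occurring at any time after the 8-week AE follow-up period up to EOS should be reported only if considered causally related". Protocol 6.1.3 sets the follow-up horizon: "all patients will enter in the follow-up period until Week 24".

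On the analysis side, SAP 8.9.1 defines TEAEs as "those AEs that start or worsen after the first dose of IMP and up to 8 weeks after the last IMP dose". Protocol 6.5.5.1.1 and 8.3.3.2 use the same 8 weeks. SAP 8.9.1 also promises a listing of all AE data. It does not mention the drug safety database, SAE reconciliation, or any output for events after the window.

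Two sections give a general recording rule with no time limit. Protocol 6.5.5.1.3 requires AEs to be recorded in the eCRF, and Protocol 6.5.5.1.4 says: "Both serious and nonserious AEs are to be reported on the AE page of the eCRF as specified in the eCRF instructions".

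**The concern.** An 8-week exposure window is a legitimate choice. The difficulty is what happens to the events that the sponsor still collects after it. These are SAEs that an investigator attributes to pegcetacoplan. They are few by construction, but they are the late events that bear most directly on the safety part of the primary objective. The plan has them reported and then routes them away from the database that feeds the tables.

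The stated reason is that study closure should not be delayed. That reason is weak for events with onset before EOS, because Protocol section 12 already has the study report wait until the database is cleaned for all visits through Week 24.

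The effect is also uneven. Patients who stop dosing early have the longest time on study outside the window. Protocol 6.3.3.1 asks that they continue follow-up visits and procedures unless consent is withdrawn.

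**Working it through.** The plan gives no figure for the length of this gap, so there is none to reproduce. The check has two parts.

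**1. Route of a non-fatal related SAE with onset after the window**

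- eCRF AE pages: no. Protocol 6.5.5.1.2 sends it only to the drug safety database.
- TEAE tables: no. It falls outside the definition in SAP 8.9.1.
- Listing of all AE data: no, unless the event has entered the study data. The SAP describes no such transfer.
- Deaths (SAP 8.9.6) and overall survival (SAP 8.8.2.4 and 8.8.2.5): not applicable, because the event is not fatal.

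A fatal event takes a different route. Protocol 6.5.7.3 collects date of and reason for death independently of AE reporting, and SAP 8.9.6 summarizes deaths by cause and lists them with no TEAE limit. The death is therefore visible, but not as a related SAE by SOC and PT.

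**2. Length of the uncovered period**

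Inputs: the window is last dose + 56 days (Protocol 6.5.5.1.2), and the Week 24 visit is Day 169 ± 3 (Table 1).

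Formula: gap = 169 − (last-dose day + 56), with a minimum of 0.

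The dosing table is not readable in the public document, so the last-dose day is an assumption. Two versions bracket it:

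- *Nominal:* the visit day at the end of treatment (Day 29, 85 or 113).
- *Reconstructed:* Days 1, 3, 5 and 8, then every 3 days. This is inferred from the AUC intervals in SAP 6.1, the expected-infusion rule in SAP 8.7.5 and the every-3-days schedule in Protocol 6.4.5. The last dose within 28, 84 or 112 days is then Day 26, 83 or 110.

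| Patient | Last dose (nominal / reconstructed) | Window ends | Days uncovered to Day 169 |
|---|---|---|---|
| 16-week completer | 113 / 110 | 169 / 166 | 0 / 3 |
| 12-week completer | 85 / 83 | 141 / 139 | 28 / 30 |
| Stops around Week 4 (assumed) | 29 / 26 | 85 / 82 | 84 / 87 |

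As a share of the 168 days from Day 1 to Day 169, a 12-week completer has 28/168 = 17% to 30/168 = 18% uncovered. The assumed early stopper has 84/168 = 50% to 87/168 = 52%. The ± 3-day visit window moves each gap by up to 3 days; for the nominal 12-week case the range is 25 to 31.

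Early stopping is expected. Protocol 8.1 estimates that 9 of 12 patients will complete at least 4 weeks, which leaves 12 − 9 = 3 who may not. Those who survive and remain on study would have gaps of about 12 weeks or more.

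**The case against.** The best defence is that the plan is consistent with its own definitions. The safety endpoint is the occurrence of TEAEs, and every definition of a TEAE stops at 8 weeks. The same 8 weeks governs contraception, anti-infective prophylaxis and pregnancy reporting. Late events are outside the endpoint by design, and they still reach the sponsor within 24 hours (Protocol 6.5.5.1.4), so oversight is not lost. Reconciliation may also be described in the data management plan or the eCRF instructions, which are not public. This stands as an argument against changing the window and against treating the point as serious. It does not explain why related SAEs already in the sponsor's hands should be absent from the AE outputs.

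A reader might infer more than the documents support:

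- **That late related SAEs vanish from all safety outputs.** They do not. Deaths appear in SAP 8.9.6 and in overall survival.
- **That Protocol 6.5.5.1.4 says the opposite of 6.5.5.1.2.** Its general sentence defers to the eCRF instructions, and the same section carries its own related-only rule for late SAEs. It is a general rule with an exception that is not cross-referenced.
- **That AE collection marked through Week 24 in Table 1 promises full recording to that visit.** Footnote m limits that row, and 16-week completers need the Week 24 entry because their window runs almost to that visit.
- **That the TEAE rate is understated, for example 0/12 instead of 1/12.** Events after the window are not TEAEs, and reporting them separately leaves the TEAE rate unchanged.

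**Conclusion.** The point holds for non-fatal SAEs judged related, with onset after the 8-week window and before EOS. Followed as written, Protocol 6.5.5.1.2 and SAP 8.9.1 leave them out of every planned AE and SAE table and listing.

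The exposed time is about 4 weeks for 12-week completers, essentially nil for 16-week completers, and about 12 weeks for a patient assumed to stop around Week 4. These figures rest on the assumed last-dose days and on the patient surviving and staying on study. They measure uncovered time, not expected events: the documents give no rate for late related SAEs, so the number omitted may well be zero.

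The conclusion also assumes that no unseen document already provides for transfer from the safety database. It is a modest reporting gap in a 12-patient descriptive pilot. It is worth closing because safety is part of the primary objective and the data already exist.

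**What to change.** 1. **Data.** At database lock, import the related SAEs reported after the window from the drug safety database through SAE reconciliation, or have sites enter them on the eCRF AE page. Amend the last sentence of the follow-up paragraph in Protocol 6.5.5.1.2 accordingly. If the protocol can no longer be amended, a listing taken from the safety database and specified in the SAP would serve.
2. **SAP 8.9.1.** Add one count line and one listing titled *Investigator-assessed related SAEs with onset more than 8 weeks after last dose up to EOS*, kept apart from TEAEs. Add a footnote that unrelated SAEs were not collected in this period.
3. **Protocol 6.5.5.1.3 and 6.5.5.1.4.** Cross-reference 6.5.5.1.2 so that sites have one unambiguous recording rule.

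The cost is a little reconciliation work and one extra output. No visits, assessments or sponsor reports are added, and the TEAE definition is unchanged. The drawback is that the listing shows a selected subset, because late SAEs judged unrelated are not required to be reported. Without the label and footnote, a reader could take it as a complete account of late SAEs.
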